For those determined to be eligible, the following will occur:

- Complete medical history and physical exam
- Baseline Blood Tests including:
 - TPN panel
 - Liver profile
 - Renal profile

- Ca
- P04
- Mg
- Triglycerides
 - Essential fatty acid levels
 - Thromboelastography (TEG) - with platelet mapping preferred
 - CBC, differential, platelets.
 - PT/PTT (at outset and then monthly)
 - Cholesterol
- Pregnancy test (urine) for females of child-bearing potential.

All patients will be followed as inpatients within the Regional Center for Neonatal Care (RCNC), the Department of Surgery, and the Division of Gastroenterology. As outpatients they will be followed within the Comprehensive Nutrition Clinic (CNC). Laboratory monitoring of patients with intestinal failure on TPN can be found on Compliance 360. Inpatients undergo the same monitoring, but a TPN panel and CBC are performed once weekly. Outpatients will undergo weekly monitoring of vital signs and fluid balance as well as inspection of gastrostomies, enterostomies, and central venous catheter exit sites by home healthcare nurses.

While they are on Omegaven® they will be seen and examined twice a month for study visits, and they will undergo blood sampling twice a month to obtain repeat levels of their baseline tests for the first 6 months. After the first 6 months, they will be seen and examined monthly and will undergo monthly blood sampling. Adverse events and concomitant medication information will be collected and documented at each study visit.

Below is a description of the study procedures:

Medical History and Physical

A complete, comprehensive history and physical will be performed at the beginning and end of the study. An interim medical history and a brief physical exam will be performed at all other study visits.

Clinical and demographic data will also be obtained to include: age, gender, race, and current medications.

At other study visits, an abbreviated physical exam will be performed and changes in medical history or concomitant medications will be noted.

Phone Calls:

For the first 6 months of the study, a study coordinator will contact research participants/families weekly to assess for any changes in health status and changes to medications. Thereafter, the coordinator will contact participants/ families monthly

approximately midway between monthly clinic visits. Changes in clinical status and concomitant medications will be monitored until the end of the study.

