Contact will occur by telephone unless subjects are seen in the clinic or are hospitalized. Applicable clinical records obtained at clinic visits and during hospitalizations such as H&Ps, labs, and medications can be used for research purposes.

Treatment with Investigational Drug

For the first two days of treatment, subjects will receive Omegaven® at 0.5 g/kg per day to assess tolerance and will progress to a maintenance dosage range of 0.8 to 1.2 g/kg/day over 12 hours at an infusion rate approximating 1 g/kg/12 hours (10 ml/kg/12 hours). The 12-hour infusion time will be used to minimize waste because of Centers for Disease Control and Prevention requirements that source containers of lipid emulsion be changed every 12 hours. Dosing is based on previously described dosing of fish-oil emulsions as monotherapy noted within the literature (8). Omegaven® will be infused intravenously through either a central or peripheral catheter in conjunction with other parenteral nutrition containing dextrose and amino acids. Omegaven® is isotonic. It is compatible with parenteral nutrition solutions and may be co-infused via y-site.

While hospitalized, serum triglyceride levels will be monitored weekly to insure that triglyceride concentrations do not exceed 1000 mg/dl during the infusion of fat emulsion. During hospitalization, coagulation studies will also be conducted weekly. PT and PTT will be conducted at baseline and then monthly. Other laboratory tests will be conducted to monitor for blood glucose metabolism, electrolyte and fluid balance and liver and kidney function in accordance with current institutional standards for monitoring hyperalimentation. Thromboelastography (prefer with platelet mapping) will be obtained at baseline and approximately 10 days prior to scheduled surgery to assess platelet aggregation dysfunction.

Urine pregnancy tests will be performed at baseline and monthly thereafter for females of child-bearing potential.

The patient will be observed for signs of metabolic overload and other adverse events. Adverse events will be documented by the study staff and may be used as a rationale for dosage adjustments of the study drug.

Study Drug Administration

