While patients are inpatients, the study drug will be administered by the CCHMC pharmacy. After patients have been discharged, the drug will be administered by Cincinnati Children's Hospital Home Care Pharmacy and/or the family. The study drug may be delivered by the Children's Hospital Home Care Service just as Intraplipid® is currently delivered or provided by the study team at the participants' outpatient appointments.

Dose Reduction:

If hypertriglyceridemia develops, operationally defined as serum triglyceride levels >1000 mg/dL, after a patient has been enrolled in the study, the following will be considered prior to reducing the dose:

1. If the level was obtained while the patient was receiving a continuous 12-hour infusion of Omegaven®, a repeat serum triglyceride level will be obtained while the patient is off the infusion just prior to resuming the infusion.
2. Other sources of hypertriglyceridemia should be considered and addressed.

If the triglycerides continue to remain high after considering the above interventions, a dosage reduction of 25% should be considered. The rationale for a twenty five percent reduction is to offer a reasonable possibility for improvement in triglyceride levels while maintaining a lipid dose high enough to prevent essential fatty acid deficiency.

Persistently elevated triglyceride values above 1000 mg/dl after 72 hours of a 25% dose reduction will result in a further 25% reduction. This process will be repeated every 72 hours until either the triglyceride levels have fallen below 1000 mg/dl or Omegaven® is stopped.

The rationale for operationally defining hypertriglyceridemia at a much higher level (>1000 mg/dl) than customarily defined (>200 mg/dl) is that levels of 200 to 1000 are commonplace among patients on TPN and intravenous lipid. These levels, while abnormal, are customarily secondary to cholestasis rather than being secondary to lipoprotein lipase deficiency, metabolic syndrome, or other causes of hypertriglyceridemia. We have chosen to make 1000 mg/dl our cut off because it is the level wherein serious complications such as pancreatitis and lipid overload syndrome may occur mandating immediate lipid reduction.

Follow-Up Assessments

(See Study Treatment Procedures Table below)

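### Above 1000 mg/dl, the triglyceride rule makes the first Omegaven reduction discretionary and undated, and its compulsory 72-hour step starts only once a reduction has been made

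*Combined protocol and SAP*

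**What the plan says.** The Dose Reduction part of Section IX.F applies once a child on study has a triglyceride above 1000 mg/dl. It has three stages.

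- **Before any reduction.** If the level was drawn during an infusion, "a repeat serum triglyceride level will be obtained while the patient is off the infusion just prior to resuming the infusion". Separately, "Other sources of hypertriglyceridemia should be considered and addressed". The second item has no time limit.
- **First reduction.** "If the triglycerides continue to remain high after considering the above interventions, a dosage reduction of 25% should be considered".
- **Later reductions.** "Persistently elevated triglyceride values above 1000 mg/dl after 72 hours of a 25% dose reduction will result in a further 25% reduction". This repeats every 72 hours until the level is below 1000 mg/dl or the drug is stopped.

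The same part explains the cut-off: "it is the level wherein serious complications such as pancreatitis and lipid overload syndrome may occur mandating immediate lipid reduction". It explains the 25% step as a reasonable chance of lowering triglycerides "while maintaining a lipid dose high enough to prevent essential fatty acid deficiency".

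On routine monitoring, Treatment with Investigational Drug (also IX.F) has weekly triglycerides in hospital "to insure that triglyceride concentrations do not exceed 1000 mg/dl during the infusion of fat emulsion". For children on study drug generally, IX.F says "they will undergo blood sampling twice a month to obtain repeat levels of their baseline tests for the first 6 months", and monthly after that. A footnote to the Study Procedures Table says weekly for laboratory tests other than PT/PTT.

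**The concern.** The reason given for the cut-off and the action attached to it do not match. The plan calls 1000 mg/dl a level at which lipid must come down at once, then leaves the first reduction to discretion with no date. The only dated, compulsory step depends on that discretionary one having been taken. An investigator can therefore follow the rule fully while a child stays on the full dose, above a level the plan itself links to pancreatitis and lipid overload, until the next routine draw. At that draw the same discretionary sentence applies again.

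What is at stake is the safety of individual children on a product that was not FDA-approved when the protocol was written. The efficacy comparison is not affected.

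**Working it through.** **1. Timing of each step, from the Dose Reduction text**

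| Step | Force | Clock |
|---|---|---|
| Off-infusion repeat, if the first level was on infusion | listed for consideration before reducing; worded as will be obtained | before the next infusion |
| Search for other causes | should | none |
| First 25% reduction | should be considered | none |
| Second reduction | compulsory | 72 h after the first |
| Third and later | compulsory | every further 72 h |

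The time from a persistent value above 1000 mg/dl to the first reduction has no upper limit. Counting from the first reduction, later ones fall at 72, 144 and 216 hours. Without a first reduction, none of these is triggered.

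**2. Does another section close the gap?** High triglycerides are not a withdrawal criterion (IX.B) and are not named in the stopping rules (IX.C). No other section compels or dates the first reduction. That the full dose continues meanwhile is an inference: the text orders no hold, and item 1 assumes the infusion will resume.

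**3. Next required triglyceride if the first reduction is withheld.** In hospital it is the weekly draw. For outpatients the interval is unclear: the IX.F text gives twice monthly and then monthly, the table footnote says weekly, and the institutional standard to which IX.D and IX.F refer is not in the documents.

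**4. Worst-case illustration**

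Inputs: 1.0 g/kg/day, within the 0.8 to 1.2 g/kg/day maintenance range; 25% steps; 72-hour intervals; a weekly draw. Assumptions: the first reduction is withheld, no unscheduled draw is taken for 7 days, and the comparison child stays above 1000 mg/dl at every re-check. The text does not say whether later 25% steps are of the starting or the current dose, so both are shown.

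- No reduction: 7 × 1.0 = 7.0 g/kg.
- Steps of the starting dose: 3 × 0.75 + 3 × 0.50 + 1 × 0.25 = 4.00 g/kg.
- Steps of the current dose: 3 × 0.75 + 3 × 0.5625 + 1 × 0.4219 = 4.36 g/kg.
- Ratios: 7.0/4.00 = 1.75 and 7.0/4.36 = 1.61.

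Multiplying by 0.8 and 1.2 gives 5.6 to 8.4 g/kg without reduction, against 3.2 to 4.8 or 3.5 to 5.2 g/kg with it.

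**5. Sensitivity to the start of the clock.** If the scheduled draw was on infusion, the off-infusion repeat can use up to about a day, leaving about 6 days to the next weekly draw. The totals are then 6 × 1.0 = 6.0 g/kg, against 3 × 0.75 + 3 × 0.50 = 3.75 or 3 × 0.75 + 3 × 0.5625 = 3.94 g/kg. The ratios are 1.60 and 1.52.

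**The case against.** The strongest defence is that this is a sensible graded rule. A first high value may reflect sampling during the infusion or another cause, so judgement comes first; once a reduction has failed for 72 hours, discretion ends. The text also treats a reduction as the expected outcome, and a careful clinician would reduce or re-check sooner. Much of this stands. It defends the confirmation step, which should be kept. It does not explain why a value that remains high after that step has neither a default action nor a date.

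Several stronger readings are tempting, and the documents do not support them:

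- **That the rule is weaker at the higher dose.** It escalates with persistence after a reduction. The difference in dose is a by-product.
- **That 61% to 75% more lipid is the expected excess.** It is correct arithmetic for a worst case. Nothing shows that the sequence is likely, and grams of lipid at the planned dose do not measure harm.
- **That outpatients would wait about 15 or 30 days.** This depends on which monitoring text governs and on a standard outside the documents.
- **That a withheld reduction escapes oversight.** Section XI gives the DSMB safety data about every 2 to 3 months, including laboratory evaluations and a list of dose adjustments. Section XII counts abnormal values that need therapy as adverse events, and a level said to mandate lipid reduction arguably qualifies. This oversight is slow for a 72-hour problem, but it exists.
- **That the sampling conditions conflict.** Screening during infusion and confirming off infusion are compatible.

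**Conclusion.** The point holds as an internal mismatch in a safety rule. The plan says the level requires immediate lipid reduction, yet the first reduction is optional and undated, and the compulsory sequence depends on it. In hospital, the rule as written allows up to about a week at full dose before another triglyceride is required. The 7.0 versus 4.0 to 4.4 g/kg comparison only illustrates that week under the stated assumptions.

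The practical weight is modest. About 25 children are planned. Those above 1000 mg/dl on 1 g/kg/day or less of Intralipid are excluded (IX.A). The documents give no frequency for values above the cut-off on Omegaven. Discontinuation for related reactions above Grade 3 (XII) and the stopping rules (IX.C) remain as protection once clinical harm appears. The change is worth making because it is cheap and concerns a level the plan itself calls dangerous. No effect on the primary analysis is claimed.

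**What to change.** Replace the sentence on the first reduction with:

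> If a level drawn off infusion (the repeat under item 1, or the first level if it was drawn off infusion) is above 1000 mg/dl, the dose will be reduced by 25% from the next infusion after the result is known, while other causes are addressed. If the investigator withholds the reduction, the reason is recorded and the off-infusion level is repeated within 72 hours.

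Add this for-cause draw as a footnote to the Study Procedures Table.

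The wording covers a first value already drawn off infusion, for which item 1 requires no repeat. It keeps the investigator's discretion but makes reduction the default. Where the reduction is withheld, the lipid given before the next required value at 1.0 g/kg/day falls from up to 7 × 1.0 = 7.0 g/kg (weekly draw) to at most 3 × 1.0 = 3.0 g/kg.

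The cost is one small extra draw when a reduction is withheld, and slightly less lipid at the first step. From 0.8 to 1.2 g/kg/day, a 25% reduction leaves 0.8 × 0.75 = 0.6 to 1.2 × 0.75 = 0.9 g/kg/day, and the plan chose that step size with essential fatty acid deficiency in mind. No change is proposed to the dose on which later reductions are based, since that is a clinical trade-off against deficiency.

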body weight per day, and who are unlikely to tolerate substantial enteral nutrition until several months following their small intestinal insult.

II. Purpose of Study

The specific aim of this study is to ascertain whether PNAC can be reversed if a fish oil-based intravenous lipid product (Omegaven®) at a dose of up to 1 g/kg body weight/day is substituted for a soy-based intravenous lipid product (Liposyn® or Intralipid®) as part of the daily TPN of infants and children with intestinal failure and PNAC. Secondary aims will be to confirm the safety of Omegaven®.

III. Background

In North America, infants and children who require parenteral nutrition (TPN) customarily receive solutions whose caloric distribution is balanced between glucose, protein, and fat to provide approximately 60-70 % of calories via glucose, 10-15 % of calories via protein, and 20-30% of calories via lipid.(1) Commercial lipid solutions utilized in North America are customarily soy-based, and contain high quantities of phytosterols including sitosterol and stigmasterol. Animal data suggest that high quantities of stigmasterol inhibit fxr, a nuclear receptor in the hepatocyte that helps to regulate bile acid homeostasis by controlling expression of bile acid export pumps. (2) Thus, exposure to a high quantity of stigmasterol is potentially hepatotoxic to individuals who have a propensity for cholestasis due to a poorly developed bile secretory process.

It is known that infants and children with underlying intestinal failure are at extraordinarily high risk for cholestasis. (3) The cholestatic process is reversible in approximately ¼ of infants with parenteral nutrition associated cholestasis (PNAC), even when soy-based lipid emulsions are given parenterally, if those infants can experience small intestinal adaptation and ultimately tolerate and assimilate the majority of their calories via enteral nutrition. Unfortunately, if adaptation does not occur rapidly enough, PNAC may progress to endstage liver disease resulting in death or necessitating combined liver/small intestinal transplantation.

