 - Impaired lipid metabolism (triglycerides >1000 mg/dL) while on 1g/kg/day or less of Intralipid
 - History of severe hemorrhagic disorders (ie. hemophilia, Von Willebrand disease, etc.)
 - Unstable diabetes mellitus
 - Collapse and shock
 - Stroke/Embolism
 - Cardiac infarction within the last 3 months
 - Undefined coma status
 - Pregnancy (positive pregnancy test) prior to enrollment in the study for females of child-bearing potential
 - Females of child-bearing potential who are unwilling to use birth control during study participation
2. Parental decision to forego the use of Omegaven®
3. Known fish or egg allergy
4. Pregnancy
5. Causes of liver disease other than PNAC

B. Withdrawal Criteria

1. Decision of an assenting minor/adult subject or parent/guardian to withdraw from the study*
2. Anaphylaxis
3. Evidence of spur cell anemia.
4. Increasing anemia (hemoglobin < 7 g/dL) in the absence of gastrointestinal bleeding.
5. Mucosal bleeding or bleeding from IV insertion sites requiring transfusion.
6. Reproducible priapism associated temporally with the infusion
7. Mucosal bleeding associated with abnormal platelet function
8. Bowel adaptation such that patient can either come off TPN or such that enteral fat can meet the patient's nutritional requirements
9. Patient undergoes liver transplantation
10. Pregnancy
11. Patient is lost to follow up

* If an assenting minor chooses to withdraw from the study early, even if the parent wants the child to participate, the child will have their wishes respected.

C. Stopping Rules

If two subjects develop the same grade-3 adverse event (including liver function tests, Protocol – Compassionate Use of a Fish Oil-derived Intravenous Fat Emulsion (Omegaven®) to Reverse Parenteral Nutrition (PN) Induced Cholestasis

coagulation profile, and platelet count) related to the study medication that is irreversible upon de-escalation (does not reverse after 10 days) or upon discontinuation of the study drug, or any subject develops a related grade-4 adverse event, these events will be the cause for termination of the study.

D. Monitoring for toxicity due to Omegaven®

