Following completion of the study medication, subjects will be seen for a final study visit within 1 month for a follow-up assessment. A complete, comprehensive history and physical will be performed. Blood samples will be collected and a urine pregnancy test will be done for females of childbearing potential. Adverse events and concomitant medications will be documented by the study staff.

The following table summarizes Study Procedures:

Study Procedures Table

	Baseline (Day 0)	Weekly while Inpatient	Weekly for first 6 months	Twice a month for the first 6 months	Monthly	Final Visit (within 1 month after treatment)
Signed informed consent/assent	X					
History	X			X	X	X
Physical Exam	X	X		X	X	X
Blood specimen (4.4 mcl using microtainers) [#]	X	X		X	X	X
Urine pregnancy test*	X				X	X
Phone calls (clinical status and concomitant medication collection)			X		X **	

At baseline and then monthly for PT/PTT. At baseline and then weekly for other laboratory studies (see Section IX, E).

* For females of child-bearing potential.

** Phone calls will take place monthly (between the monthly visits)

G. Data Collection

Demographic and clinical information will be collected whenever clinical data are available via uniform baseline and follow up clinical data extraction forms to ensure accuracy and consistency. The essential demographic information includes age at diagnosis, gender, race and ethnicity, birth history, past medical history, and family history. The clinical information includes presence or absence of jaundice, hepatosplenomegaly, or ascites.

H. Compensation

Participants will not be compensated for study participation. Subjects will receive study medication, clinical supplies, and laboratory evaluations that are obtained outside the standard of care free of charge.

I. Withdrawal

Protocol – Compassionate Use of a Fish Oil-derived Intravenous Fat Emulsion (Omegaven[®]) to Reverse Parenteral Nutrition (PN) Induced Cholestasis

Data collected from patients who withdraw from the study will be included in the final analysis using intent to treat. Patient enrollment will continue until all 25 patients complete all requested study requirements outlined. It will be recommended that patients withdrawn from the protocol resume a reduced lipid intake, treat infections promptly as they occur and advance feedings as quickly as tolerated.

X. Assessment of Efficacy

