The primary endpoint will be reduction in conjugated or direct bilirubin level to below 1 mg/dl. Data from previous retrospective analyses and prospective uncontrolled studies suggest that from the inception of Omegaven® therapy, conjugated or direct bilirubin will remain elevated for approximately 8 weeks at levels comparable to those observed prior to administration of Omegaven®. Subsequently, levels are expected to fall by approximately 1 mg/dl/week until they normalize. The time to normalization will vary according to each patient's baseline conjugated or direct bilirubin level. Thus, a patient who begins Omegaven® with a conjugated or direct bilirubin level of 7 mg/dl is likely to experience normalization within 14 weeks (8+6 weeks). We will compare the group receiving Omegaven® with historical controls from our internal registry who have demonstrated cholestasis while on Intralipid®. We will compare changes in conjugated/direct bilirubin concentration over time between groups via Kaplan-Meier analysis (see Statistics section XIII).

Secondary endpoints will be: normalization of total bilirubin and liver enzymes. Differences in these values at the end of 14 weeks of therapy will be compared with those of controls via Kaplan-Meier analysis identical to that employed for conjugated and direct bilirubin levels. Furthermore, we expect that elevated triglyceride levels which might be present at the initiation of therapy will have normalized at the same time that liver profiles have normalized.

XI. Assessment of Safety/Data Safety Monitoring Board

A DSMB will monitor the study for the occurrence of adverse events (both serious and otherwise). A significant increase in the rate of adverse events would be cause for concern for the safety of participants in the study. Information on adverse events will be presented in several ways: (1) listings of serious adverse events with accompanying narrative summary by the PI; (2) summaries of adverse events by body system and type of event. This information will be presented to the DSMB.

The DSMB will also monitor the efficacy and the conduct of the study. Interim monitoring reports for the DSMB will include, but will not be limited to, such tabulations as:

1. platelet counts
2. essential fatty acid profiles
3. coagulation studies
4. liver profiles

5. renal profiles

The DSMB will meet at least once per year and possibly more frequently given the expected speed of recruitment and study medication administration.

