All adverse events will be followed until they are resolved or the patient's participation in the treatment ends (i.e., until a final report is completed for that patient).

In addition, all SAEs and those non serious events assessed by the Investigator as attributable (i.e. possibly, probably, definitely related to the drug) will continue to be followed even after the patient's participation in the treatment is over. Such events will be followed until they resolve or until the Investigator assesses them as "chronic" or "stable." Resolution of such events is to be documented in the CRF.

XIII. Statistics

We selected a study number of 25 patients (5 patients a year for 5 years) even though, statistically, a number of 19 will be satisfactory based upon power analysis. We know from our current registry that 10% of historic controls will experience resolution of cholestasis within 8 weeks while receiving Intralipid®, and we know from the data of Gura, et al (5) that approximately 50% of experimental subjects will experience resolution of cholestasis within eight weeks while receiving Omegaven®. Thus, achieving an alpha of 0.05 and a beta of 0.80, a sample size of 19 patients and 19 controls will be adequate (11). However, insofar as this is a compassionate release protocol, we will not refuse entry into the study even if we have shown statistically that Omegaven® is efficacious. We estimate that at most we will acquire five patients per year, and we anticipate that within five years, Omegaven® or SMOF (soy, MCT, olive oil and fish oil) parenteral lipids will have obtained FDA approval for clinical use.

The analysis populations will include (1) subjects receiving Omegaven® under this protocol and (2) historical controls from our internal registry who have demonstrated cholestasis while on Intralipid®. Paired t-tests will be used to report the statistical significance of differences between means. A p value of 0.05 or less will be considered significant. Wilcoxon Tests will be used to report the statistical significant differences between medians, and χ^2 tests/Fisher's exact tests will be used to report proportions. A Kaplan-Meier analysis will compare changes in conjugated/direct bilirubin concentration over time between groups. Cox proportional hazard models will be used to estimate crude and adjusted hazard ratios. Analyses will be performed via SAS 9.2 (SAS Institute Inc, Cary, NC) and S-Plus 8.1.1 (Insightful, Inc, Seattle, WA).

IX. Data Management

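### The primary event does not require the native liver, and the Kaplan-Meier plan does not treat death or liver transplant as competing events, so a resolution probability read from the curve is too high if these children are censored

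*Combined protocol and SAP*

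**What the plan says.** All references are to the combined protocol and SAP.

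- **Aim (II).** "The specific aim of this study is to ascertain whether PNAC can be reversed", where PNAC is parenteral nutrition associated cholestasis.
- **Primary endpoint (X).** "The primary endpoint will be reduction in conjugated or direct bilirubin level to below 1 mg/dl". No native-liver condition is attached.
- **Course of the disease (III).** If the bowel does not adapt fast enough, "PNAC may progress to endstage liver disease resulting in death or necessitating combined liver/small intestinal transplantation". No frequency is given.
- **Withdrawal criteria (IX.B).** The list includes "Patient undergoes liver transplantation". It also includes "Bowel adaptation such that patient can either come off TPN". Death is not on the list.
- **Withdrawn patients (IX.I).** "Data collected from patients who withdraw from the study will be included in the final analysis using intent to treat". Nothing says whether they count as not resolved, are censored, or are followed on later bilirubin values.
- **Analysis (XIII).** "A Kaplan-Meier analysis will compare changes in conjugated/direct bilirubin concentration over time between groups". Section X says much the same. Cox models are named for hazard ratios, and chi-square or Fisher's "exact tests will be used to report proportions". No censoring or competing-event rule is stated for any of them.

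**The concern.** A child who has died or received a new liver can no longer reverse PNAC in the native liver. Ordinary Kaplan-Meier censors such a child, and so treats the child as still able to resolve at the same rate as those who remain. One minus the Kaplan-Meier estimate (1-KM) then answers a hypothetical question and exceeds the proportion of children who actually resolve.

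The endpoint wording opens a second gap. It asks only for a bilirubin value, so it does not exclude one taken after transplant, which would reflect the graft.

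At stake is any absolute probability of resolution read from the curves, on Omegaven or in the registry controls. It would depend on a rule that is not written down and could be chosen after the data are seen.

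**Working it through.** **Inputs from the documents.** 25 treated subjects; 19 per group in the sample-size statement; resolution within 8 weeks of about 50% on Omegaven and 10% in controls (all XIII).

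**Assumed.** The number and timing of deaths and transplants, since the documents give no rate.

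**The plan's own figure.** For 10% versus 50%, two-sided alpha 0.05 and power 0.80 (the stated beta of 0.80 read as power), the pooled-variance formula gives

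n = [1.96·√(2·0.3·0.7) + 0.842·√(0.1·0.9 + 0.5·0.5)]² / 0.40² = 19.4,

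which rounds up to 20 per group. At 19 per group the power is 79.2%. The stated 19 is reproduced closely, and this point does not touch it.

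**Effect of censoring in one group.** Take n = 25 with 12 resolved. With no other censoring, the Aalen-Johansen cumulative incidence is 12/25 = 48%, which is also the result when dead or transplanted children are kept as not resolved. If k such children are censored after j of the 12 resolutions,

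1-KM = 1 − [(25 − j)/25] × [(25 − k − 12)/(25 − k − j)].

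| k | Timing | Calculation | 1-KM |
|---|---|---|---|
| 3 | before any resolution | 1 − 10/22 | 54.5% |
| 3 | after 6 | 1 − (19/25)(10/16) | 52.5% |
| 3 | after 10 | 1 − (15/25)(10/12) | 50.0% |
| 3 | after all 12 | 12/25 | 48.0% |
| 1 | before any resolution | 1 − 12/24 | 50.0% |
| 1 | after all 12 | 12/25 | 48.0% |

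The standard error of 48% is √(0.48·0.52/25) = 0.100, or 10 points.

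**Check by another route.** Under proportional cause-specific hazards, 1-KM = 1 − (1 − R − D)^(R/(R+D)), where R and D are the cumulative incidences of resolution and of death or transplant. With R = 50%, an assumed D of 5%, 10%, 15%, 20% or 25% gives 51.6%, 53.4%, 55.4%, 57.7% or 60.3%. With R = 10%, the excess is only 0.3 to 1.6 points over the same range.

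**Which timing is plausible.** Section X expects about 8 weeks without change and then a fall of about 1 mg/dl per week. From the entry minimum of 3 mg/dl, that puts normalisation at about week 8 + 2 = 10 or later, so a death or transplant in the first 8 weeks would precede every resolution. Section XIII assumes half resolve within 8 weeks, which implies smaller shifts.

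**Between groups.** Take 19 controls with 2 resolved: 2/19 = 10.5%, or 2/16 = 12.5% if 3 are censored early. With all kept as not resolved, the difference is 48.0 − 10.5 = 37.5 points.

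| Early events censored | Difference in 1-KM (points) | Shift |
|---|---|---|
| 3 on Omegaven only | 54.5 − 10.5 = 44.0 | +6.5 |
| 3 in each group | 54.5 − 12.5 = 42.0 | +4.6 |
| 1 on Omegaven, 3 in controls | 50.0 − 12.5 = 37.5 | 0.0 |
| 3 in controls only | 48.0 − 12.5 = 35.5 | −2.0 |

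Shifts are taken from unrounded values. They are the largest within each group for these counts; later events shift that group less.

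**The case against.** The strongest reply is that the plan promises a between-group comparison and does not say that 1-KM will be reported as a probability. Proportions go to chi-square or Fisher tests, whose natural denominator is everyone enrolled, and section IX.I invokes intent to treat. In one ordinary sense of that term, a child who dies or is transplanted is simply not resolved, and there is no overestimate. This stands as a limit on reach: the error follows only if these children are censored and a probability is then read from the curve. It does not close the gap. Section IX.I gives no scoring rule, and it does not clearly reach deaths, since death is not a withdrawal criterion.

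The size is also fairly challenged. No event rate is given, three events is an invented count, and even the largest shift shown for it (6.5 points) is below one standard error. This too stands. The shift is nonetheless systematic, and an unwritten rule can be chosen late.

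Three stronger readings are tempting, and the documents support none of them.

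- **That the plan inflates the advantage of Omegaven.** The illustrative shifts run from −2.0 to +6.5 points, depending on which group has more events and when. If the events are censored, the Cox hazard ratio remains a valid cause-specific comparison.
- **That transplanted children will be counted as successes.** Each one scored on a normal post-transplant value would add 1/25 = 4 points, and three would give 15/25 = 60%. Blood is drawn at a final visit within a month of treatment, so such a value could exist. But the aim of reversing PNAC, and one sense of intent to treat, speak against scoring it so. The wording fails to exclude this reading; it does not adopt it.
- **That the estimate is too high overall.** Withdrawal for bowel adaptation is a different case, in which censoring may push the estimate down. The point here covers death and transplant only.

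**Conclusion.** The concern holds in a conditional form. The primary event lacks a native-liver condition, and the Kaplan-Meier plan lacks a competing-event rule for two outcomes that the protocol itself foresees. If children who die or are transplanted are censored, a resolution probability taken from the curve is too high whenever such an event precedes a later resolution. The counts used here give an excess of 0 to 2 points for one such child and 0 to 6.5 points for three. Those counts are assumptions, so the true size is unknown and could be negligible. The direction of any effect on the group difference is not determined, and the sample size is not in question. This should be corrected because the rule is cheap to state now and open to choice later. It is not a fatal flaw. Sections X and XIII, where the rule belongs, contain none; one elsewhere, in parts of the document that I have not seen, cannot be excluded.

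**What to change.** In sections X and XIII, and identically for subjects and registry controls:

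1. Define the primary event as the first conjugated or direct bilirubin below 1 mg/dl with the native liver in place.
2. Exclude post-transplant bilirubin from every efficacy analysis.
3. Treat death, or any transplant that includes the liver, before the event as a competing event. Show the Aalen-Johansen cumulative incidence in place of 1-KM, and describe the Cox model as cause-specific.
4. Count these children as not resolved in the planned chi-square or Fisher comparison, and say so in IX.I, so that intent to treat has a defined meaning.

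A single sentence doing step 4 would remove much of the ambiguity for the proportions, but would leave the curves unresolved. Other withdrawal reasons, bowel adaptation among them, need their own stated rule.

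The cost is a few sentences and slightly more analysis. The practical condition is data. It must be confirmed that the control registry holds dates of death and transplant. The same dates are needed for subjects who withdrew earlier for another reason, because under section XII follow-up after participation ends is limited to serious and attributable adverse events, and a later death or transplant may not be captured.
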